12.2.8 Safety Analysis(es)

Adverse events will be tabulated according to the current version of the MedDRA.

Frequencies and percentages will be presented overall, for each system organ class, and for each preferred term. Summaries of treatment-emergent AEs, treatment-related AEs, AEs leading to discontinuation, and serious AEs will be presented for each of the test products.

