4.6.1 Adverse Events and Serious Adverse Events

All AEs will be reviewed by the Clinical Research Scientist or Designee prior to database lock and will be coded to a system organ class (SOC) and preferred term (PT) using the Medical Dictionary for Regulatory Activities (MedDRA). During this review stage, AEs will be further categorized as skin or non-skin.

Treatment emergent adverse events (TEAEs) are defined as new AEs that occur on or after the first product application. Adverse events with an onset date/time prior to the first product application will be considered as non-treatment emergent.

Treatment emergent adverse events will be summarized by the number and percentage of subjects having any AE, an adverse event in each System Organ Class, and each Preferred Term. The following summary tables and listings will be presented by product:

- Table of TEAEs by SOC and PT (PPD [REDACTED]).
- Table of TEAEs by SOC, PT and severity (PPD [REDACTED]).
- Table of TEAEs by skin/non-skin and PT (PPD [REDACTED]).
- Table of treatment emergent treatment-related AEs by SOC and PT (PPD [REDACTED]).
- Table of treatment emergent treatment-related AEs by SOC, PT and severity (PPD [REDACTED]).
- Table of treatment emergent treatment-related AEs by skin/non-skin and PT (PPD [REDACTED]).
- Table of treatment emergent treatment-related serious adverse events (SAEs) by SOC and PT (PPD [REDACTED]) [only produced if there are more than 5 treatment emergent SAEs].
- Table of treatment emergent treatment-related non-serious SAEs by SOC and PT (PPD [REDACTED]) [only produced if there are more than 5 treatment-emergent SAEs].
- Listing of all AEs (PPD [REDACTED] for all randomized subjects; PPD [REDACTED] for non-randomized subjects).

- Listing of deaths (PPD [redacted]).
- Listing of non-fatal SAEs (PPD [redacted]).
- Listing of treatment emergent AEs leading to study or product discontinuation (PPD [redacted]).
- Listing of treatment-emergent AEs classified as skin (PPD [redacted]).

In the event that there is nothing to report, a null listing will be produced.

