4.7 Analysis of Other Variables

No other analyses will be performed for this study.

5 Changes to the Protocol Defined Statistical Analysis Plan

Any changes from the originally planned statistical analysis specified in the protocol are outlined in [Table 5-1](#).

Table 5-1 Changes to Protocol Defined Analysis Plan

Protocol	Reporting & Analysis Plan	
Statistical Analysis section	Statistical Analysis Plan	Rationale for Changes

 • Section 6.8: Medication/treatments taken within 30 days of signing the informed consent form will be documented as a prior [redacted] medication/treatment. Medications/treatments taken after signing the informed consent form will be documented as concomitant medication/treatments. 	
 • The current standard definition of the prior medication and concomitant medications has been used in the Reporting and Analysis plan: Prior medications are defined as those which stopped before the first application of the study product. Concomitant medications are defined as the medication ongoing or started on or after the first application of the study product. 	
 • To maintain the current standard definition of prior medication and concomitant medications • Importantly, all medications/therapies concomitant to study participation will be provided. • For this study, signing the informed consent form and the first application of the study product will be on the same day. Thus, the variance in definitions will not impact the overall analysis of the prior and concomitant medications.

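### SAP 4.6.1 cuts back the by-product summaries of discontinuation AEs and serious AEs that protocol 12.2.8 promises, and names a self-contradictory table; none of this is declared in Table 5-1

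*SAP*

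**What the plan says.** Protocol 12.2.8 states: "Summaries of treatment-emergent AEs, treatment-related AEs, AEs leading to discontinuation, and serious AEs will be presented for each of the test products". The sentence before it sets the form: "Frequencies and percentages will be presented overall, for each system organ class, and for each preferred term". It sets no minimum count and does not restrict serious events to related ones.

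SAP 4.6.1 opens its output list with "The following summary tables and listings will be presented by product". For the two categories at issue, the list contains:

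- **AEs leading to discontinuation:** "Listing of treatment emergent AEs leading to study or product discontinuation". There is no table.
- **Serious AEs:** "Table of treatment emergent treatment-related serious adverse events (SAEs) by SOC and PT", with the condition "only produced if there are more than 5 treatment emergent SAEs". Deaths and non-fatal SAEs are also listed.
- **A further table:** "Table of treatment emergent treatment-related non-serious SAEs by SOC and PT", under the same condition on the SAE count.

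SAP Section 5 says: "Any changes from the originally planned statistical analysis specified in the protocol are outlined in" Table 5-1. That table has one entry, on the definitions of prior and concomitant medication.

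**The concern.** The safety objective covers both serums, and its endpoint is the frequency and severity of AEs. The protocol promises four by-product AE summaries. The SAP delivers two of them as tables (TEAEs and treatment-related AEs) and reduces the other two without saying so.

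The discontinuation summary has some weight in this trial. The success percentage is computed in completed subjects and missing data are not imputed, so a woman who stops early may contribute no final score. A by-product count of AE discontinuations is one place where she could still be seen.

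The table of non-serious SAEs is a separate drafting fault. Programmed literally, it selects nothing. Read as a slip, it is still switched on by a count of events that it does not display.

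**Working it through.** **Step 1. Compare commitment with delivery.**

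| Protocol 12.2.8 summary | SAP 4.6.1 output | Match? |
|---|---|---|
| Treatment-emergent AEs | Tables by SOC/PT, by severity, by skin/non-skin | Yes |
| Treatment-related AEs | The same three tables for related events | Yes |
| AEs leading to discontinuation | Listing only | No: no n (%), no SOC/PT table |
| Serious AEs | Table of related SAEs only, and only above the trigger; listings otherwise | No: narrowed twice |

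The SAP itself separates summary tables from listings, so a listing is not the promised frequency-and-percentage summary. No all-causality SAE table is planned under any condition. If the trigger fires, it does so on all treatment-emergent SAEs, while the table then shows only the related ones.

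**Step 2. Non-serious SAEs.** Protocol 10.2 defines an SAE as an AE whose outcome is serious. A non-serious SAE therefore cannot exist, and the class is empty if taken literally. If AEs was meant, the class is not empty, but the table still depends on the number of SAEs.

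**Step 3. Declaration.** Table 5-1 has only the medication-definition entry. Neither reduction in Step 1 appears there.

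**Step 4. How likely is the trigger to fire?** The plan states no SAE rate, so there is no figure to reproduce.

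Inputs:
- n = 90 randomized (protocol 12.1, SAP 1.4), all assumed to receive product and so to be in the Safety population.
- More than 5 means at least 6 SAEs. At one each, 6/90 = 6.7% of subjects.
- The per-subject SAE rate p over 21 (+2) days is an assumption and is varied.
- At most one SAE per subject, subjects independent (assumption).

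Formula: P(X ≥ 6) = 1 − Σ C(90, k) p^k (1 − p)^(90 − k), summed over k = 0 to 5.

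| Assumed p | Expected SAEs (90p) | P(trigger fires) |
|---|---|---|
| 0.5% | 0.45 | 0.0007% |
| 1% | 0.9 | 0.03% |
| 2% | 1.8 | 1.0% |
| 3% | 2.7 | 5.4% |
| 5% | 4.5 | 29% |
| 10% | 9.0 | 90% |

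The chance reaches 5% at a rate of about 2.9% and 50% at about 6.3%.

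**The case against.** The strongest reply is that this is a matter of reporting format and that no information is lost. Much of that stands.

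- SAP 4.6.1 keeps by-product listings of all AEs, deaths, non-fatal SAEs and AEs leading to discontinuation. Serious TEAEs are also counted in the unconditional TEAE tables, including the one by severity. With few events, a reader can count from the listings. Anyone who infers that serious events are dropped or hidden goes further than the documents allow.
- A reader might infer that the report will contain no count of women who stopped because of an AE. SAP 4.1.1 plans a disposition table with numbers and percentages by reason for discontinuation, and protocol 10.7 requires AE withdrawals to be distinguished from others. That table is not stated to be by product, covers leaving the study rather than stopping product, and has no SOC/PT. It covers part of the promised summary but does not replace it.
- A reader might infer that the trigger can never fire. The documents give no SAE rate, and the answer moves from negligible to 29% between assumed rates of 1% and 5%. The SAP also does not say whether the trigger counts events or subjects. If it counts events, several SAEs in one woman make firing more likely.
- It is tempting to size the problem by the dropout that the plan tolerates: 90 randomized for 60 completers allows 30 to leave. That is all-cause dropout and does not measure AE discontinuation. Moreover, reactions that fit the cutaneous or ocular grading scales are not AEs unless judged unusual (protocol 5.8, 9.2.1, 9.2.2). A woman who stops for ordinary gradable irritation may therefore be missing from an AE-discontinuation table too. The table helps with the completer problem but does not solve it.
- Protocol 12.2.8 promises no table of non-serious AEs, so the faulty title breaks no commitment. It is an evident slip.

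None of this answers the mismatch with protocol 12.2.8, the contradiction in the title, or the silence of Table 5-1.

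**Conclusion.** The plan is wrong as written; severity is minor. Two of the four AE summaries promised in protocol 12.2.8 are reduced in SAP 4.6.1: one to a listing, the other to related SAEs behind a count threshold. One further table has a self-contradictory title and a trigger that does not match its evident content. Table 5-1 records none of it. These conclusions follow from the text and need no assumption.

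That the SAE threshold is unlikely to be reached in about 90 healthy women over three weeks does rest on an assumption, namely a per-subject SAE rate of no more than about 3% with one SAE per subject. The supportable statement is unlikely, not impossible.

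The effect is confined to how safety results are tabulated. The primary endpoint, the success rule and the sample size are untouched, and every event remains in the report.

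**What to change.** In SAP 4.6.1:

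1. Add a table of TEAEs leading to product or study discontinuation, n (%) by product, SOC and PT, produced unconditionally.
2. Add a table of all treatment-emergent SAEs, n (%) by product, produced unconditionally, with related events identified.
3. In the title of the non-serious table, change SAEs to AEs, keep the restriction to treatment-related events, and remove the SAE-count trigger. Dropping the restriction as well would change the table's content on a guess about intent.

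If the sponsor prefers to keep any reduction from protocol 12.2.8, enter it in Table 5-1 with a reason.

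The cost is SAP wording and up to three short tables from data already collected. It needs no protocol amendment, no further subjects and no new data.

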4.7 Analysis of Other Variables

No other analyses will be performed for this study.

5 Changes to the Protocol Defined Statistical Analysis Plan

Any changes from the originally planned statistical analysis specified in the protocol are outlined in [Table 5-1](#).

Table 5-1 Changes to Protocol Defined Analysis Plan

Protocol	Reporting & Analysis Plan	
Statistical Analysis section	Statistical Analysis Plan	Rationale for Changes

 • Section 6.8: Medication/treatments taken within 30 days of signing the informed consent form will be documented as a prior [redacted] medication/treatment. Medications/treatments taken after signing the informed consent form will be documented as concomitant medication/treatments. 	
 • The current standard definition of the prior medication and concomitant medications has been used in the Reporting and Analysis plan: Prior medications are defined as those which stopped before the first application of the study product. Concomitant medications are defined as the medication ongoing or started on or after the first application of the study product. 	
 • To maintain the current standard definition of prior medication and concomitant medications • Importantly, all medications/therapies concomitant to study participation will be provided. • For this study, signing the informed consent form and the first application of the study product will be on the same day. Thus, the variance in definitions will not impact the overall analysis of the prior and concomitant medications.
